4.2. Controls

The healthy control subjects will be searched in a broad social network of colleagues, family, friends and acquaintances of the study participants and/or researchers and will be matched with the general ICU population for age, sex and BMI. Control subjects with a recent history of treatment with HPA-axis interfering drugs will be excluded. Any relationship with the researchers is never of that kind that there is a situation of “dependency”. In no way is there any kind of pressure on patients or volunteers. At all times every measure is taken to guarantee a free decision. Every individual can withdraw his/her consent at any time prior or during the study.

4.3. Expected duration of the study

a. Time window of monitoring per patient:

Patients from each cohort will be studied during a total period of 4.5 hours, with repetitive blood sampling during 2 consecutive mornings from 10.45-13.00 h, after receiving an alternate injection of CRH or placebo each morning. To use the crossover design, the effects of the intervention during the first period (i.e. effect of CRH) must not carry over into the second period.¹⁶ Firstly, taking the half-life of hCRH (30.5 +/- 3.3 min) into account, the requirement for a wash-out of 5 times the drug half-life (152.5 min) is sufficient to meet this assumption.¹⁷ Secondly, based on the fact that the cortisol clearance is reduced with at least 50% in critical ill patients than in healthy individuals, it is justifiable to perform the second alternate injection on the morning after the first injection.¹

b. Calculated sample size:

Based on the available literature⁹, we calculated to require 20 patients per cohort in order to detect a potential Cushing-like suppression of the ACTH response to CRH in critically ill patients, in comparison with the response of 20 healthy volunteers, with an alpha error of 1% (to correct for the multiple comparisons of each of the 3 patient cohorts with the healthy controls) and >80% power. In more detail: we expect an effect size of 1.20 based on previous findings, reporting a difference of mean delta AUC ACTH of 2159 to 795 pmol L⁻¹ min, with a common standard deviation of 1136 pmol L⁻¹ min.⁹ Power calculation was performed with an independent T-test for comparison of 2 means, assuming equal variances.

To take into account a potential increase in variation due to the heterogenous critical illnesses, we will double the number of patients to 40 per cohort. With 40 patients per cohort, we can detect a reduction of 30% in the ACTH responses to CRH between 2 patient cohorts, with an alpha error of 5% and >80% power (power calculation was performed as explained above, based on a reduction of 30% of 2159 pmol L⁻¹ min with the same standard deviation⁹). Recruitment of patients will continue until the preset number of 40 patients is reached in the 3 patient cohorts, with equal proportions of ICU admission categories among the groups.

c. Study duration:

Based on a retrospective analysis of the mean stay of patients in the ICU, we estimate that the study will take approximately one year to finalize recruitment.

5. Study Procedures and sample collection

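### The >80% power for a 30% difference between two patient cohorts leaves out the extra patient variation that was the reason for enrolling 40 per cohort

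*Protocol*

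**What the plan says.** Section 4.3 b of the protocol contains two calculations.

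The first compares a patient cohort with healthy controls. It rests on a cited study, "reporting a difference of mean delta AUC ACTH of 2159 to 795 pmol L⁻¹ min". The SD taken from that study is 1136 in the same units. The result is 20 patients per cohort against 20 volunteers at an alpha of 1%. The number of patients is then raised to allow for a "potential increase in variation due to the heterogenous critical illnesses, we will double the number of patients to 40 per cohort". No larger SD is given.

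The second follows at once and concerns two patient cohorts: "With 40 patients per cohort, we can detect a reduction of 30% in the ACTH responses to CRH between 2 patient cohorts". The power claimed is above 80% at a 5% alpha. Its stated basis is "based on a reduction of 30% of 2159 pmol L⁻¹ min with the same standard deviation". The method is the same as in the first calculation, an independent t-test with equal variances. Neither calculation says whether the test is one-sided or two-sided.

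Section 3.1 gives the primary objective as comparing responses across increasing duration of critical illness, and also against matched controls. Section 7 names, for the cohorts, only comparisons with the healthy reference group.

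**The concern.** One sentence treats greater spread among patients as likely enough to justify twice the recruitment. The next quotes power for those same 40 patients as if the spread had not grown. In the comparison with controls, at most one of the two groups has the extra variation. Between two cohorts both groups have it, so this is the comparison it would hurt most.

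The cohort-to-cohort contrast bears directly on the primary objective, that is, whether the ACTH response changes with time in ICU. If it comes out null, a reader holding a stated power above 80% for a 30% change may conclude that no such change exists. That inference is safe only if the power holds under the plan's own premise about patient variation.

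**Working it through.** **Inputs**, all from section 4.3 b: means 2159 and 795; SD 1136; 20 vs 20 at alpha 1%; 40 vs 40 at alpha 5% for a 30% reduction; equal-variance t-test. The SD multipliers below are assumptions, because the protocol gives none.

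**Formula.** Noncentrality = difference / (SD × √(1/n₁ + 1/n₂)), with n₁ + n₂ − 2 degrees of freedom. Power is the noncentral t probability beyond the critical value.

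**1. First calculation.** Difference 2159 − 795 = 1364, and 1364 / 1136 = 1.20, as stated. At 20 vs 20 and alpha 1%, power is 85.4% two-sided and 90.9% one-sided. The claim of more than 80% holds on either reading.

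**2. Second calculation as stated.** Difference 0.30 × 2159 = 647.7, and 647.7 / 1136 = 0.570. Noncentrality = 647.7 / (1136 × √(2/40)) = 647.7 / 254.0 = 2.55, with 78 degrees of freedom.
- One-sided 5%: power 81.1%; 39 per cohort would be enough for 80%.
- Two-sided 5%: power 71.2%; 80% needs 50 per cohort.

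The protocol's figure is therefore reproduced, but only with a one-sided test.

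**3. Reserve in the second calculation.** Solving for the SD that gives exactly 80% at 40 vs 40:
- One-sided: 1155, which is 1.7% above 1136.
- Two-sided: 1021, which is 10% below 1136.

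**4. Larger patient SD, 40 vs 40, alpha 5%.** The detectable difference has 80% power and scales with the SD; percentages are of 2159.

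| SD multiplier (assumed) | SD | Power for 648, one-sided | Power for 648, two-sided | Detectable difference, one-sided | Detectable difference, two-sided |
|---|---|---|---|---|---|
| 1.00 | 1136 | 81.1% | 71.2% | 637 (29.5%) | 721 (33.4%) |
| 1.10 | 1250 | 74.3% | 62.9% | 701 (32.5%) | 793 (36.7%) |
| 1.20 | 1363 | 67.8% | 55.5% | 765 (35.4%) | 865 (40.0%) |
| 1.414 | 1607 | 55.7% | 42.9% | 901 (41.7%) | 1019 (47.2%) |

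The last row is a doubled variance (√2 = 1.414), the increase that a doubled sample offsets exactly when both groups double.

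**5. Reserve against controls.** At 40 vs 20, SD 1136, two-sided alpha 1%, noncentrality = 1364 / (1136 × √(1/40 + 1/20)) = 1364 / 311.1 = 4.38 and power is 95.4%. It stays at 80% or more up to a common SD about 1.25 times larger, or about 1.71 times if only the patients' SD rises (normal approximation).

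**The case against.** The best defence has four parts.

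- **One sample may serve two comparisons.** This stands. A reader might infer that the extra 20 patients are spent twice, but the text does not support that. The doubling follows from the comparison with controls and does its work there. If only the patients' variance doubles, 40 patients give the same standard error as 20 did before.
- **The assumption is disclosed.** This also stands. The sentence says the calculation was done "with the same standard deviation", and it does not claim that the power survives greater spread. Disclosure makes the mismatch visible but does not resolve it, because the claim that the trial "can detect a reduction of 30% in the ACTH responses to CRH between 2 patient cohorts" carries no condition.
- **No sum is wrong.** On a one-sided reading the figure reproduces at 81.1%. The fall to 71% comes from reading the unstated sidedness as two-sided and has nothing to do with variation. It must be kept apart from the main point.
- **The formal tests lie elsewhere.** Section 7 names comparisons of the cohorts with controls only, and the protocol nowhere says that a null cohort contrast will be taken as proof of no change. This lowers the severity. It does not remove the point, because section 3.1 puts duration of illness in the primary objective and section 4.3 b chose to state a power for it.

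It may also be said that any design sized just above 80% has a thin margin. That is true, but here the plan has just said that it expects the assumption under that margin may fail.

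**Conclusion.** The point holds at moderate severity. The stated cohort-to-cohort power has essentially no room for the extra variation that section 4.3 b itself anticipates. An SD more than 1.7% above 1136 takes it below 80% even one-sided. With a two-sided test it does not reach 80% at SD 1136 at all.

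How far the power falls depends on an SD increase that the protocol does not quantify. The figures of 56% one-sided and 43% two-sided belong to an assumed doubling of variance and are not estimates of the trial's power. Nor do the documents support reading the trial as too small for its sizing comparison: the required number came from the comparison with controls, which holds with reserve. This is not a matter left to a statistical analysis plan, since the protocol states the power figure itself.

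**What to change.** Amend the second power statement in section 4.3 b, without adding patients:

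1. State the sidedness. If the test is two-sided, the power at SD 1136 is 71%, not more than 80%.
2. Either say that the cohort-to-cohort figure assumes no increase in variation over 1136, or name the patient SD allowed for and give the power or the detectable difference at that SD. The table above supplies values for both readings, for example a difference detectable with 80% power of 765 one-sided or 865 two-sided if the SD is 20% larger. The sponsor should choose and justify the SD, since the protocol gives no basis for any particular one.
3. Say that the reserve from doubling applies to the comparison with controls.
4. Say that a null cohort-to-cohort result will be interpreted through its confidence interval and not through the planned power.

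The cost is protocol wording only. Sample size, endpoints and tests do not change, but one stated power becomes less favourable or explicitly conditional.

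### The stated power above 80% for a 30% reduction between two patient cohorts holds only for an undeclared one-sided 5% test; two-sided, 40 per cohort gives 71%

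*Protocol*

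**What the plan says.** Protocol section 4.3 b makes two power statements.

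The first compares each patient cohort with 20 healthy volunteers. It uses means of 2159 and 795 pmol/L min, "with a common standard deviation of 1136 pmol L⁻¹ min", an alpha of 1% and power above 80%, and arrives at 20 patients per cohort. The method is given: "Power calculation was performed with an independent T-test for comparison of 2 means, assuming equal variances".

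The number is then raised to allow for "a potential increase in variation due to the heterogenous critical illnesses, we will double the number of patients to 40 per cohort".

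The second statement follows at once and describes what cohorts of this size achieve: "we can detect a reduction of 30% in the ACTH responses to CRH between 2 patient cohorts, with an alpha error of 5" per cent. The power claimed is above 80%. The calculation uses the same method and is "based on a reduction of 30% of 2159 pmol L⁻¹ min with the same standard deviation".

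Neither statement says whether the test is one- or two-sided, and nothing else in the protocol does. Section 7 plans an ANOVA of the delta AUC values, comparing each cohort with the healthy group under a Bonferroni correction. It declares no one-sided test.

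**The concern.** An alpha of 5% with no further qualification is ordinarily read as two-sided. On that reading the protocol's own inputs do not give power above 80%.

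The scientific question does not suggest a one-sided test either. Section 2 considers that longer feedback inhibition may suppress CRH and ACTH further, but also that the axis may progressively lose its sensitivity to feedback. Section 3.1 likewise leaves open whether suppression persists or is lost.

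This is the only power statement for differences between patient cohorts, and section 3.1 puts the response with increasing duration of illness into the primary objective. If the cohorts do not differ significantly, a reader who trusts the protocol will take the chance of missing a 30% reduction to be below 20%. Two-sided, it is about 29%.

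There is a second problem in the same lines. The protocol spends the doubling from 20 to 40 on an expected increase in variation, then calculates what 40 can detect as if there were no increase.

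**Working it through.** **Inputs, all from protocol section 4.3 b**
- 40 patients in each of two cohorts; alpha 5%; independent t-test with equal variances
- Difference: 0.30 × 2159 = 647.7 pmol/L min
- Standard deviation: 1136 pmol/L min

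**Formula.** Standardised difference d = difference / SD. Noncentrality δ = d × √(n/2) for n per group, with 2n − 2 degrees of freedom. Power is the probability that a noncentral t variable exceeds the critical value (in absolute value if two-sided).

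**Step 1: the first statement, as a check of the method.** d = (2159 − 795)/1136 = 1.20. With 20 against 20 and alpha 1%, power is 85.4% two-sided and 90.9% one-sided. Both exceed 80%, so the statement reproduces, but it does not show which kind of test was used.

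**Step 2: the second statement.** d = 647.7/1136 = 0.570; δ = 0.570 × √20 = 2.55; 78 degrees of freedom.

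| Test at 5% | Critical t | Power, 40 per cohort | Smallest n per cohort for 80% |
|---|---|---|---|
| One-sided | 1.665 | 81.1% | 39 |
| Two-sided | 1.991 | 71.2% | 50 |

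The stated figure reproduces one-sided only. Two-sided, 49 per cohort gives 79.8% and 50 gives 80.6%. A normal approximation gives 72.2% for 40 per cohort, so the choice of formula does not explain the gap.

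**Step 3: what 40 per cohort can detect at two-sided 5% and 80% power.** This needs d = 0.634, so the difference is 0.634 × 1136 ≈ 721 pmol/L min, and 721/2159 = 33%.

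**Step 4: the standard deviation.** The protocol gives no standard deviation for patients, so the increases below are assumptions chosen to show a range. The last one is what doubling the sample exactly offsets: δ depends on √n / SD, so twice the patients balances an SD larger by √2 = 1.41.

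| SD relative to 1136 | One-sided 5% | Two-sided 5% |
|---|---|---|
| 1.00 | 81.1% | 71.2% |
| 1.02 | 79.8% | 69.5% |
| 1.10 | 74.3% | 62.9% |
| 1.25 | 64.7% | 52.2% |
| 1.41 | 55.7% | 42.9% |

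Even one-sided, an increase of 2% takes power below 80%.

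**The case against.** The strongest reply is that the figure is not an arithmetic slip. A one-sided 5% t-test gives 81.1%, and the target is worded as a reduction. That explains where the number may have come from, and it stands to this extent: the calculation can be reproduced, and the documents do not show a computing error. It does not rescue the sentence. Wording an effect as a reduction does not declare a directional test; no such test appears anywhere; and section 2 gives reasons to expect change in either direction.

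Stronger readings are tempting, but the documents do not support them:

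- **That 40 per cohort rests on this figure.** It does not. Section 4.3 b obtains 40 by doubling 20; the 30% sentence then describes what 40 can detect.
- **That the whole primary objective lacks a valid power statement.** Comparison with healthy controls is also part of that objective (section 3.1) and is the first analysis in section 7. Its power statement reproduces.
- **That power should be judged at an alpha corrected for three pairs of cohorts.** The Bonferroni correction in section 7 is for the three comparisons with healthy controls, and section 4.3 b sets 5% for this one.
- **That 30% should be taken of an already suppressed patient mean.** The base of 2159 is openly stated. A patient cohort at the Cushing-like mean is a possibility under study, not a planning assumption for this comparison.

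It is also fair to say that the larger standard deviations in the working are illustrations. The inconsistency over variation does not depend on them: it lies in the protocol's own consecutive sentences.

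**Conclusion.** Wrong as written. The claimed power above 80% requires a one-sided 5% test that the protocol neither declares nor motivates. At two-sided 5%, 40 per cohort has 71% power for 648 pmol/L min and reaches 80% at 721, so the detectable reduction moves from 30% to 33% of 2159.

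The shortfall is about 9 percentage points below the stated 80%. It rests on the protocol's own difference, standard deviation and test, with two-sided testing as the natural reading. If the sponsor did intend a one-sided test, the figure is right by a narrow margin, but the test would have to be declared and justified.

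On either reading, the statement makes no allowance for the larger variation among patients that the doubling was meant to cover. The sample size of 40 and the power statement against healthy controls are not called into question by this point.

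**What to change.** Keep 40 per cohort. In protocol section 4.3 b, replace the sentence on the 30% reduction with wording such as: With 40 patients per cohort, a two-sided alpha of 5% and a standard deviation of 1136 pmol/L min, power is 71% for a difference of 648 pmol/L min between two patient cohorts (30% of 2159) and 80% for a difference of 721 pmol/L min (33% of 2159); these figures make no allowance for a larger standard deviation in patients.

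The cost is one reworded passage and a slightly less favourable figure. No patients are added and no analysis changes.

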5.1 Patients group

After informed consent, each patient from each cohort will be randomized for the order of CRH or placebo injection into two crossover study groups. Consecutive patients will be randomly assigned to 'first placebo' or 'first CRH' using blinded envelopes, stratified according to the 3 'time in ICU' cohorts. At 11.00 am, after 2 baseline blood samples (EDTA, 4ml) (-15 and 0 min), 100µg CRH or placebo (0.9% NaCl) will be injected as an intravenous bolus. Blood samples (EDTA, 4ml) will then be obtained at 5, 10, 15, 30, 45, 60, 90, and 120 minutes after injection to determine plasma ACTH and cortisol concentrations. The next day, each patient will receive the alternate injection, and the same blood sampling protocol as the day before (Figure 1). Since for each participant the measured effect is the difference between the response to the injection of CRH and placebo, variability is reduced.¹⁶

Injections of CRH or placebo will be given through a peripheral or central venous catheter, followed by a flush with ±5 ml (depending on the distance between the injection point and the insertion point of the catheter) of normal saline (NaCl 0.9%) to guarantee a full injection of the entire dose, and blood samples are drawn from an arterial or central venous catheter, all in situ and inserted for clinical purposes. The total amount of blood sampled per session is 40ml (Good Clinical Practice (GCP) consists of 40 ml per day). Some patients may experience mild, brief facial flushing immediately after injection, but at this dose level no other side effects have been reported.¹⁸ Allergic reactions have also not been reported.

[figure not shown]

Figure 1: Study protocol. Patients from the 3 cohorts will be randomized for the order of CRH or placebo injection into two crossover subgroups. Each patients from each subgroup will be studied during a total period of 4.5 hours, with repetitive blood sampling during 2 consecutive mornings from 10.45-13.00 a.m.

The ACTH and cortisol responses to CRH/placebo will be correlated with available demographic and clinical data.

Such stored patient data include:

Patient characteristics and outcome parameters: demographics (age, gender, BMI), medical history (diabetes, malignancy, renal replacement therapy), admission characteristics (reason for ICU admission, APACHE II score, SIRS and sepsis on admission), patient characteristics during ICU stay (clinical evidence of adrenal failure, SIRS and sepsis), ICU and hospital stay, ICU and hospital mortality.

Clinical parameters: Among others vital parameters (mean, systolic and diastolic blood pressure, pulse, temperature), mechanical ventilation, mean daily glycemia and renal function (daily urinary volume, creatinine clearance), infection.

Treatment information: all relevant treatments such as vasopressors and inotropes, treatment with opioids, anti-coagulants, insulin, and types and amounts of nutrients.

5.2 Control group

Time profiles of ACTH and cortisol response to exogenous CRH are not clearly defined in the literature. Especially data from healthy volunteers with a comparable age, gender and BMI as our patient population are lacking. To compare the evolution of the ACTH and cortisol response during critical illness with healthy reference values, we will use the same study protocol as for the patients in 20 demographically matched healthy volunteers, with repetitive blood sampling during 2 consecutive mornings from 10.45-13.00 h, after receiving an alternate injection of CRH or placebo each morning. Volunteers will be asked to limit their morning nutritional intake to a European breakfast.

6. Compensation for control group

Healthy control subjects will be compensated for all expenses made to participate in the study, such as transportation cost and costs for parking space, and will be offered a meal on each study day and an overnight stay in Leuven. Furthermore, a gift card (value card worth 50 EUR) will be offered as an additional reward.

7. Statistics

First, the response to CRH injection (changes over time in plasma ACTH and cortisol concentrations) will be corrected for its corresponding placebo test result (changes over time in plasma ACTH and cortisol concentrations), resulting in a delta AUC value. The delta AUC values will be compared between each of the 3 cohorts and the healthy reference group, with correction for multiple comparisons with use of ANOVA (Bonferroni correction of the alpha error to correct for the multiple comparisons of each of the 3 patient cohorts with the healthy controls), after transforming the data to normally distributed values if needed. If the latter is not possible, non-parametrical tests will be used.

Second, for those patients from whom multiple CRH test results were collected, changes in delta AUC values within these patients will be analyzed with use of mixed models / repeated measures ANOVA after transforming the data to normally distributed values if needed.

Third, correlations between the ACTH and cortisol responses to exogenous CRH and clinical risk and outcome parameters will be done with the use of Pearson tests. Fourth, these measurements will be compared in patients with a favorable and a non-favorable clinical outcome.

8. Ethics and regulatory approvals

The study will be conducted in compliance with the principles of the Declaration of Helsinki (2008), the principles of GCP and in accordance with all applicable regulatory requirements. This protocol and related documents is will be submitted for review to Ethics Committee.

The study can and will be conducted only on the basis of prior informed consent by the subjects, or their legal representatives, to participate in the study. We will obtain a signed informed consent form (ICF) for all patients prior to their enrollment and participation in the study in compliance with all applicable laws, regulations and the approval of the Ethics Committee. We will retain such ICFs in accordance with the requirements of all applicable regulatory agencies and laws.

The investigators shall treat all information and data relating to the study disclosed to the Investigators in this study as confidential and shall not disclose such information to any third parties or use such information for any purpose other than the performance of the study. The collection, processing and disclosure of personal data, such as patient health and medical information is subject to compliance with applicable personal data protection and the processing of personal data (Directive 95/46/EC and Belgian law of December 8, 1992 on the Protection of the Privacy in relation to the Processing of Personal Data).

Total blood loss per patient will be limited to 80 ml (GCP is 40 ml per day). Samples will be taken via the arterial line or central venous catheter, already in place as part of the standard of care for ICU monitoring, and thus no additional discomfort will be caused.

All laboratory measurements specifically required for this study will be performed in the Laboratory of Intensive Care Medicine and will thus not generate any cost for the patients or healthy control subjects.

9. Data Management

For reasons of data integrity and internal control during data input, the patient name will be stored in a separate table linked to the eCRF (electronic Case Report Form). However, these data will only be accessible for the authorized local research staff and the principal database manager on an individual login/password base. When the database is finalized, the identity data will be detached from the eCRF and stored at the local site. Data transferred within the research group will always be anonymous and limited to the data needed to address the question of the researcher.

10. References

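### The ANOVA of delta AUC in Section 7 has no term for the randomised order of CRH and placebo, so any day-to-day change adds to the error variance

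*Protocol*

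**What the plan says.** **Order.** In Section 5.1, "each patient from each cohort will be randomized for the order of CRH or placebo injection into two crossover study groups". The method is: "Consecutive patients will be randomly assigned to 'first placebo' or 'first CRH' using blinded envelopes, stratified according to the 3 'time in ICU' cohorts". No block size is given. The gap is one day: "The next day, each patient will receive the alternate injection".

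**Controls.** Section 5.2 says "we will use the same study protocol as for the patients in 20 demographically matched healthy volunteers". It does not say whether their order is randomised in a stratum of its own.

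**Analysis.** Section 7 states that the CRH response "will be corrected for its corresponding placebo test result (changes over time in plasma ACTH and cortisol concentrations), resulting in a delta AUC value". It continues: "The delta AUC values will be compared between each of the 3 cohorts and the healthy reference group", by ANOVA with a Bonferroni correction, after transformation if needed and with non-parametric tests as the fallback. Sequence and period are not mentioned. The sample size in Section 4.3 b rests on an independent two-sample t-test, also without such a term.

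**Carry-over.** Section 4.3 a sets the condition that "the effects of the intervention during the first period (i.e. effect of CRH) must not carry over into the second period". It offers two supports: five half-lives of hCRH (152.5 min), and then, "based on the fact that the cortisol clearance is reduced with at least 50% in critical ill patients than in healthy individuals", the conclusion that the next morning is acceptable for the second injection. No cortisol half-life or wash-out time is given.

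**The concern.** Section 5.1 justifies the crossover on the ground that taking each person's CRH-minus-placebo difference cuts variability. Differencing removes stable between-person variation, but not a change between the two days. Such a change could come from recovery, from deterioration or from the first session itself. It raises delta AUC in people who had placebo first and lowers it by the same amount in people who had CRH first. Order is randomised and known, so this spread can be explained. The ANOVA as written leaves it in the residual.

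At stake is precision, above all for the cohort-versus-cohort contrast, which has the least power to spare. If the order split happens to differ between groups, the day effect also shifts the estimated contrast in that particular trial.

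A second, smaller matter is the cortisol argument in Section 4.3 a. Slower clearance prolongs any cortisol released by the first injection, so by itself it cannot support the absence of carry-over.

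**Working it through.** **Inputs.** From Section 4.3 b: SD of delta AUC 1136; means 2159 and 795; 30% of 2159 = 647.7 (all pmol/L·min); alpha 1% against controls and 5% between cohorts; 40 per cohort and 20 controls. From Section 4.3 a: hCRH half-life 30.5 min. The day effect p is not in the protocol and is assumed to be 0, 0.25 or 0.5 SD (0, 284, 568). The 1136 is taken as the SD within a sequence.

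**1. The plan's own figures.** (2159 − 795)/1136 = 1.20. With 20 per group and two-sided alpha 1%, the t-test has 85.4% power, so the claim of more than 80% reproduces. For the 30% contrast, 647.7/1136 = 0.570. With 40 per group and alpha 5%, power is 71.2% two-sided and 81.1% one-sided. The claim of more than 80% therefore reproduces only one-sided, and the protocol does not state sidedness. Two-sided figures are used below.

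**2. How the day effect enters.** Let τ be the true CRH-minus-placebo response and p the change from day 1 to day 2.

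- Placebo first: D = τ + p + error
- CRH first: D = τ − p + error

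With equal sequences the mean is τ and Var(D) = 1136² + p². The SD is multiplied by √(1 + (p/1136)²).

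**3. Size without a sequence term.**

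| p (SD units) | SD factor | Power, 40 v 40, 30% contrast, 5% | Power, 40 v 20 controls, 1% |
|---|---|---|---|
| 0 | 1.000 | 71% | 95% |
| 0.25 | 1.031 | 69% | 94% |
| 0.5 | 1.118 | 62% | 89% |

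The loss of effective sample size is 1 − 1/(1 + 0.25²) = 6% at p = 0.25 SD and 1 − 1/(1 + 0.5²) = 20% at 0.5 SD.

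**4. Simulation of 40 v 40, balanced order, 4,000 trials per setting.** At p = 284 and 568, power was 68% and 62% without the sequence term and 71% with it. The estimated contrast stayed close to 647.7 in every case. Under the null, the test without the term rejected in 4.7% and 3.0% of trials: it is conservative, not inflated.

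**5. Unequal order splits.** The shift in a contrast is 2p times the difference in the proportion given placebo first. For 24/16 against 20/20 and p = 284, this is 2 × 284 × (0.6 − 0.5) = 57, or 9% of 647.7. Under simple randomisation, the SD of this shift at 40 v 40 is 284 × √(1/40 + 1/40) = 63.5. This is the same p² variance as in step 2 and must not be counted again.

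**6. Carry-over.** Let λ be the effect of CRH that persists into a day-2 placebo test. Then D = τ − p − λ for CRH first, and the group mean becomes τ − λ/2. If λ differs between groups by an assumed 400, the contrast is biased by 400/2 = 200. The simulation gave 201 without the sequence term and 196 with it, with type I error of 12.8% and 11.5%. A common sequence term does not cure this.

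**7. Is carry-over likely?** For hCRH, 1440/30.5 = 47 half-lives lie between injections, and 1440/152.5 = 9.4 times the stated wash-out. For cortisol, assume a normal half-life of 60 to 120 min, doubled to 120 to 240 min by halved clearance. From the last sample at 13.00 to the next session at 10.45 is 1305 min, so the fraction left is between 2^(−1305/120) = 0.05% and 2^(−1305/240) = 2.3%.

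**The case against.** The strongest reply is that Section 7 is an outline and excludes nothing, and that a sequence term may stand in an analysis plan that is not shown. This limits the point to what the protocol states. But Section 7 does state the primary model, and that model leaves out a factor the design randomises. Naming the factor improves a stated method and is more than filling in detail.

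The assumed day effect also has no source in the documents. This stands. At 0.25 SD the loss is slight, and even at 0.5 SD the comparison with controls keeps 89% power, above the stated 80%. The case is stronger for the cohort-versus-cohort contrast, which starts at 71% two-sided.

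A reader might infer more than the documents support:

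- *That group differences are biased.* A day effect common to all groups does not bias them in expectation. Bias needs a realised imbalance in order, or a day effect or carry-over that differs by group. Stratified envelopes suggest some control of balance, although no block size is given.
- *That carry-over is present.* It is not shown. The gap far exceeds the hCRH wash-out, and residual cortisol is small over the assumed range. Persisting changes in feedback or in pituitary responsiveness are not addressed, so carry-over is not ruled out either.
- *That the cortisol argument runs backwards.* It can be read as the reason for waiting until the next morning instead of only 152.5 min. On either reading it lacks a figure showing that the wait is long enough.
- *That controls fall outside the randomisation.* Section 5.2 puts them under the patients' protocol; only their stratum is unstated.

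**Conclusion.** The point holds as a matter of precision. The analysis written in Section 7 does not use the randomised order, so a systematic day effect p adds p² to the error variance. The cost is negligible if p is near zero, small at 0.25 SD (SD up 3%, power 71% to 69% for the 30% contrast) and material at 0.5 SD (SD up 12%, power down to 62%). A sequence term recovers nearly all of this and removes the chance shift from unequal order splits. These figures assume an SD of 1136 within sequence, two-sided tests, a day effect common to all groups and no carry-over.

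The documents do not support a claim of biased group contrasts or of demonstrated carry-over, and a sequence term would not correct carry-over that differs by group. The cortisol sentence in Section 4.3 a is a secondary matter of wording and of a missing figure.

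**What to change.** 1. In Section 7, analyse delta AUC with group and sequence (CRH first or placebo first) as factors. If the non-parametric fallback is used, stratify the test by sequence. Cost: about one degree of freedom.
2. Report pre-injection ACTH and cortisol on day 2 (the −15 and 0 min samples) by sequence and group, as a descriptive check on carry-over. The samples are already planned.
3. Do not adjust for the difference in baseline between the two days. The day-2 baseline is measured after the first injection and could itself carry its effect.
4. State in Section 5.2 that the healthy controls are randomised to order in a stratum of their own. Cost: one more set of envelopes.
5. Reword the cortisol sentence in Section 4.3 a so that reduced clearance is not offered as support for the absence of carry-over, and give the cortisol wash-out figure on which the sponsor relies.

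None of this needs new samples or participants.
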